2.8.3 Other safety data

2.8.3.1 ECG and cardiac imaging data

ECG data will be analysed based on central laboratory reported results. The summaries will include all ECG assessments performed no later than 30 days after the last date of study drug. All ECG assessments will be listed, and those collected later than 30 days after on treatment period will be flagged in the listing.

Selecting Primary QT Correction for Heart Rate

The analysis of QT data is complicated by the fact that the QT interval is highly correlated with heart rate. Because of this correlation, formulas are routinely used to obtain a corrected value, denoted QTc, which is independent of heart rate. This QTc interval is intended to represent the QT interval at a standardized heart rate. Several correction formulas have been proposed in the literature. For this analysis we will use some of those methods of correction, as described below. The QT interval corrected for heart rate by the Bazett's formula, QTcB, is defined as

$$QTcB = \frac{QT}{\sqrt{RR}},$$

the QT interval corrected for heart rate by the Fridericia's formula, QTcF, is defined as

$$QTcF = \frac{QT}{\sqrt[3]{RR}},$$

where RR represents the RR interval of the ECG, in seconds.

Although Bazett's correction is the historical standard, it does not perform well when heart rate fluctuates. Fridericia's formula may perform better under these conditions. An alternate correction to achieve the goal of getting uncorrelated QTc and RR is based on linear regression methods which yield, theoretically, uncorrelated QTc and RR.

Linear regression method:

- Fit a model $QT = a + b * RR$ to baseline data
- Use the estimated slope, \hat{b} , to correct QT
- Corrected QT for heart rate will be computed as follows:

$$QTcP = QT + \hat{b} * (1 - RR)$$

Data will be summarized using QTcF and QTcB. However, if these are not appropriate for the data set due to an observed large correlation between corrected QT and HR using the baseline assessments, the results will also be summarized using QTcP.

ECG Summaries

The following analyses will be performed for each applicable ECG parameters (RR, PR, QRS, QT, ventricular rate -denoted as HR in what follows-, and QTc) as noted.

- Pearson correlation between QT and RR, QTc (QTcB, QTcF and, if applicable, QTcP) and HR using individual (non-averaged) baseline assessments and separately using on-treatment assessments
- For each of the ECG parameters (HR, and QTc, QT, QRS and PR intervals) descriptive statistics at baseline, at each post-baseline time point and changes from baseline at each post-baseline time point
- For each of the QTc and QT intervals, shift tables based on notable parameter categories (≤ 450 , $>450 - \leq 480$, $>480 - \leq 500$, >500 ms) at baseline and the worst post-baseline value observed

The number and percentage of subjects with notable ECG values will be presented by treatment arm.

- QT parameter (QT, QTc) increase from baseline >30 ms, >60 ms
- Newly occurring post-baseline QT parameter > 450 ms, > 480 ms, > 500 ms
- HR increase from baseline $> 25\%$ and value > 100 bpm
- HR decrease from baseline $> 25\%$ and value < 50 bpm
- PR increase from baseline $> 25\%$ and value > 200 ms
- Newly occurring post-baseline PR > 200 ms and ≤ 220 ms, > 220 ms
- QRS increase from baseline $> 25\%$ and value > 110 ms
- Newly occurring post-baseline QRS > 110 ms and ≤ 120 ms, > 120 ms

The denominator to calculate percentages for each category is the number of patients with both a baseline and a post-baseline evaluation. A newly occurring post-baseline ECG notable value is defined as a post-baseline value that meets the criterion post-baseline but did not meet the criterion at baseline

- Frequency counts and percentages of patients with newly occurring post-baseline qualitative ECG abnormalities (morphology) will be summarized. The denominator to calculate percentages for any newly occurring ECG abnormality, each abnormality type and each individual finding is the number of patients with both a baseline and a post-baseline

evaluation, and baseline being normal, i.e. those patients who are at risk of developing this abnormality. A newly occurring post-baseline qualitative ECG abnormality is defined as a post-baseline abnormal finding which was not present at baseline

Patients with notable ECG interval values and newly occurring qualitative ECG abnormalities will be listed by treatment group, patient and timepoint, and the corresponding notable values and abnormality findings will be included in the listings.

Unscheduled ECG measurements will not be used in computing the descriptive statistics for change from baseline at each post-baseline time point. However, they will be used in the analysis of notable ECG changes and the analysis of notable QT parameters.

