- **Bradycardia:** asymptomatic cases of bradycardia have been observed in patients treated with LDK378 in clinical studies. Repeated ECG tracings will be performed throughout the study to closely monitor cardiovascular safety. Risk will also be minimized by monitoring concomitant use of other agents known to cause bradycardia (e.g., beta-blockers, non-dihydropyridine calcium channel blockers, clonidine, and digoxin) to the extent possible. Heart rate and blood pressure will also be monitored regularly during the study.
- **Hyperglycemia:** events of hyperglycemia (all grades) have been reported in less than 10% of patients treated with LDK378 in clinical studies; 5% of patients reported a grade 3/4 event. The risk of hyperglycemia was higher in patients with diabetes mellitus and/or concurrent steroid use. Patients will be closely monitored throughout the study for any signs and symptoms related to elevated blood glucose levels. Risk will be minimized by including subjects with fasting plasma glucose levels < 175 mg/dL (< 9.8mmol/L) at screening (see exclusion #3).

- **Gastrointestinal toxicity:** diarrhea, nausea, and vomiting have been very commonly reported; 12.2% of patients reported a grade 3/4 event of diarrhea, nausea, or vomiting. Risk to patients will be minimized during the study by closely monitoring symptoms and managing patients using standards of care, including anti-diarrheals, anti-emetics, or fluid replacement, as indicated.
- **Pancreatitis (including lipase and amylase elevations):** in most cases, pancreatic enzyme elevations have been mild to moderate, and have typically reversed with interruption of LDK378. Few patients have experienced pancreatitis with severe upper abdominal pain. Patients will be monitored closely for any related signs and symptoms. In order to minimize the risk to patients during the study, patients with a history of pancreatitis or a history of increased lipase or amylase levels that was due to pancreatic disease will be excluded. In addition, serum amylase must be  $\leq 2$  x ULN and serum lipase must be within normal limits at screening.

[figure not shown]

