## 5 Population

### 5.1 Patient population

This study with LDK378 as a single agent will be conducted in patients, aged 12 months to less than 18 years, with malignancies carrying a genetic alteration of ALK. Taking into account the distribution of ALK abnormalities in pediatric malignancies, it is expected that most patients will have neuroblastoma, ALCL, IMT, and rhabdomyosarcoma.

The investigator or designee must ensure that only patients who meet all the following inclusion and none of the exclusion criteria are offered treatment in the study.

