#### **7.2.2.2 Vital signs**

Vital signs (heart rate, blood pressure and temperature) will be obtained in the same position, as appropriate prior to any blood collection.

Note: Vital signs may be performed within 4 days prior to the start of a cycle and  $\pm 1$  day for other visits.

Vital signs to be obtained:

- Screening/baseline.
- Cycle 1 Day 1 (pre-dose).
- Cycle 1 Day 8 and 15.
- Cycle 2 and subsequent cycles Day 1.
- End of treatment.

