**Table 7-4 Central ECG collection plan**

| Cycle                          | Day              | Time   | ECG Type       |
|--------------------------------|------------------|--|----------------|
| Screening/
Baseline | -28 to -1 | Anytime   | 12 Lead |
| 1                              | 1                | Post-dose 4 hours (ECG should be performed just prior to drawing PK sample if both are scheduled simultaneously) | 12 Lead        |
| 1                              | 1                | Post-dose 6 hours (ECG should be performed just prior to drawing PK sample if both are scheduled simultaneously) | 12 Lead        |
| 2                              | 1                | Post-dose 4 hours (ECG should be performed just prior to drawing PK sample if both are scheduled simultaneously) | 12 Lead        |
| 2                              | 1                | Post-dose 6 hours (ECG should be performed just prior to drawing PK sample if both are scheduled simultaneously) | 12 Lead        |
| 3                              | 1                | Pre-dose (ECG should be performed just prior to drawing PK sample if both are scheduled simultaneously)          | 12 Lead        |
| 4                              | 1                | Pre-dose (ECG should be performed just prior to drawing PK sample if both are scheduled simultaneously)          | 12 Lead        |
| 5-16                           | 1                | Pre-dose   | 12 Lead        |
| Even #
cycles ≥18           | 1                | Pre-dose   | 12 Lead        |
| EOT                            | 1                | Within 14 days (up to 21 days) of last dose  | 12 Lead        |

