2.8.1.1 Adverse events of special interest

Adverse events of special interest (AESIs) are defined as AEs within the following categories/groupings of preferred terms:

- Hepatotoxicity
- Interstitial lung disease/Pneumonitis
- QT prolongation
- Hyperglycemia
- Bradycardia
- GI toxicity (nausea, diarrhea, vomiting)
- Pancreatitis (including Lipase or amylase increases)

AESIs are defined at the project level and may be updated based on emergent data to reflect new AESIs of interest at the time of analysis. The AESIs listed above will be identified based on a list of preferred terms. The list of preferred terms will be finalized in a separate document.

Frequency counts and percentages of patients with DLTs will be tabulated by treatment group based on the DDS. DLTs will be listed by treatment group and patient.

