2.8.3.2 Vital signs

Vital sign assessments will be performed in order to characterize basic body function. The parameters collected are weight (kg), body temperature (°C), pulse rate (beats per minute), systolic and diastolic blood pressure (mmHg).

Vital signs shift table based on values classified as notable low, normal, notable high or notable (high and low) at baseline and worst post-baseline will be produced for pulse rate.

Patients with clinically notable vital sign abnormalities will be listed. All vital sign assessments will be listed by patient and vital sign parameter. In the listings, clinically notable values will also be flagged.

The criteria for clinically notable values are defined in [Table 2-2](#).

Table 2-2 Clinically notable vital sign ranges.

Body temperature (°C)	High	≥39.1°C	
	Low	≤35.0°C	
Weight	High	Increase from baseline ≥ 10%	
	Low	Decrease from baseline ≥ 10%	
Pulse rate (beats per minute)	High ²	12-18 months	> 140
		18-24 months	> 135
		2-3 years	> 128
		3-4 years	> 123
		4-6 years	> 117
		6-8 years	> 111
		8-12 years	> 103
	Low ²	12-15 years	> 96
		15-18 years	> 92
		12-18 months	< 103
		18-24 months	< 98
		2-3 years	< 92
		3-4 years	< 86
		4-6 years	< 81
6-8 years	< 74		

8-12 years	< 67
12-15 years	< 62
15-18 years	< 58

¹[Systolic](#) and diastolic blood pressure will be listed individually.

²Fleming S, Thompson M, Stevens R, et al. Normal ranges of heart rate and respiratory rate in children from birth to 18 years of age: a systematic review of observational studies. Lancet 2011; published online March 15. DOI: 10.1016/S0140-6736(10)62226-X.

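### ECG heart-rate flags use fixed limits of 50 and 100 bpm from 12 months to under 18 years, so the low flag can rarely count a young child

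*SAP*

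**What the plan says.** The population is "aged 12 months to less than 18 years" (Protocol 5.1). SAP 2.8.3.1 lists the notable ECG values to be counted by treatment arm. For ventricular rate there are two rows: "HR decrease from baseline $> 25\%$ and value < 50 bpm" and "HR increase from baseline $> 25\%$ and value > 100 bpm". Neither varies with age.

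SAP 2.8.3.2, Table 2-2, defines notable pulse rate in nine age bands. A shift table on those limits "will be produced for pulse rate", and notable values are listed. The SAP does not apply these limits to the ECG heart rate and does not say why the two displays differ.

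Bradycardia is one of the adverse events of special interest in SAP 2.8.1.1. That section says: "The AESIs listed above will be identified based on a list of preferred terms". The bradycardia paragraph in Protocol 2.6 relies on repeated ECG tracings and adds: "Heart rate and blood pressure will also be monitored regularly during the study".

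**The concern.** The SAP accepts that one notable limit cannot serve all ages for pulse, then applies one to the same quantity measured by ECG. A limit of 50 bpm lies 53 bpm below the SAP's own low pulse limit at 12-18 months (103 - 50) but only 8 bpm below it at 15-18 years (58 - 50). Toddlers and adolescents share a row that toddlers can hardly enter, so a count near zero could be read as reassurance about an event of special interest.

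Timing adds to this. The first-cycle vital signs are scheduled for "Cycle 1 Day 1 (pre-dose") in Protocol 7.2.2.2, and no post-dose pulse reading is specified. The Cycle 1 Day 1 and Cycle 2 Day 1 ECGs in Protocol Table 7-4 are at 4 and 6 hours after the dose; the first entry reads "Post-dose 4 hours (ECG should be performed just prior to drawing PK sample if both are scheduled simultaneously"). For those tracings the low row is the only planned patient count of low heart rate by value.

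**Working it through.** **Inputs.** ECG limits of 50 and 100 bpm and the 25% change condition (SAP 2.8.3.1); low limit L and high limit H for each band (SAP Table 2-2). The documents give no baseline heart rates, so I assume baseline b lies between L and H, and show L, the midpoint (L + H)/2, and H. The plan states no figure of its own to reproduce.

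**Which condition decides the low row.** The 25% fall is the stricter condition only if 0.75 × b < 50, that is b < 66.7 bpm. That is under the low limit of every band up to 8-12 years (L = 67). For in-range baselines below age 12, the 50 bpm limit alone decides.

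**Fall needed under the current low row** = max(25%, 1 - 50/b). **With Table 2-2 limits** = max(25%, 1 - L/b). For 12-18 months the current rule gives 1 - 50/103 = 51.5%, 1 - 50/121.5 = 58.8% and 1 - 50/140 = 64.3%; with Table 2-2 at the high end, 1 - 103/140 = 26.4%.

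| Age band | L / midpoint / H (bpm) | Current rule, fall needed from L / midpoint / H | Table 2-2 limit, fall needed from midpoint / H |
|---|---|---|---|
| 12-18 months | 103 / 121.5 / 140 | 51.5 / 58.8 / 64.3% | 25 / 26.4% |
| 2-3 years | 92 / 110 / 128 | 45.7 / 54.5 / 60.9% | 25 / 28.1% |
| 4-6 years | 81 / 99 / 117 | 38.3 / 49.5 / 57.3% | 25 / 30.8% |
| 8-12 years | 67 / 85 / 103 | 25.4 / 41.2 / 51.5% | 25 / 35.0% |
| 15-18 years | 58 / 75 / 92 | 25 / 33.3 / 45.7% | 25 / 37.0% |

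The four bands not shown follow the same pattern. In all nine, a fall just over 25% from the midpoint lands below L.

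**Example, low row.** At 12-18 months, 121 to 80 bpm is 1 - 80/121 = 33.9%. It is not counted on ECG, although 80 is 23 bpm below the pulse limit of 103.

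**High row.** The 100 bpm limit adds something to a 25% rise only if 1.25 × b < 100, that is b < 80. Every band up to 4-6 years has L of at least 81, so for in-range baselines there the limit does no work.
- At 12-18 months, 103 to 130 bpm (130/103 - 1 = 26.2%) is flagged, although 130 is below the high limit of 140.
- At 15-18 years, 70 to 95 bpm (95/70 - 1 = 35.7%) is not flagged, although 95 is above 92.

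**The case against.** The text and arithmetic are not in dispute. The case against concerns consequence.

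- **Pulse flags cover much of the ground.** The pulse shift table has no 25% condition and uses the worst post-baseline value, including unscheduled readings (SAP 5.5.1), so a toddler with a pulse of 80 is counted there. Pulse is also taken on Days 8 and 15 of Cycle 1 and Day 1 of each later cycle. From Cycle 3 the scheduled on-treatment ECGs are pre-dose at the same visits. The gap is therefore four ECGs per patient. This stands.
- **Exposure.** Protocol 1.2.1.2.4 gives an adult half-life of 31-41 hours and an accumulation ratio of 6.2 by Cycle 2 Day 1. With one compartment and rapid absorption, the steady-state trough-to-peak ratio is about 0.63 (36-hour half-life, 2^(-24/36)) to 0.84 (1 - 1/6.2), so later pre-dose pulse readings fall at higher exposure than the first-dose peak. This weakens the Cycle 1 Day 1 argument, if adult kinetics carry over and the effect follows concentration. The Cycle 2 Day 1 post-dose ECGs still have no matching pulse reading.
- **Other routes on ECG.** Newly occurring qualitative ECG abnormalities are counted, and clinically significant ECG findings, or those leading to a dose change, become adverse events. Heart rate is summarised at each time point and all ECGs are listed. However, the qualitative count has no stated heart-rate criterion, adverse-event entry depends on judgement, and the statistics and listings give no patient count.
- **The fix has its own limits.** From a mid-range baseline the Table 2-2 limit adds nothing to the 25% change, and the SAP does not say what those limits represent or that they suit ECG ventricular rate. That is a fair reason to allow a stated justification instead. Even so, every rate flagged under the fix would be outside the SAP's own age range, which is not true of the 100 bpm row in toddlers.
- **The high row is a small matter in older children.** The mismatch is 3 bpm at 8-12 years, 4 bpm at 12-15 and 8 bpm at 15-18. This stands; the substance is in the youngest bands.
- **No reclassification count is possible**, because the documents give neither an age distribution nor baseline rates. This also stands.

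**Conclusion.** The concern holds. The ECG low-rate row is close to inert in young children: from an in-range baseline, a fall of 51-64% is needed at 12-18 months and 38-57% at 4-6 years, against 25-46% at 15-18 years. For the youngest bands the conclusion does not depend on where in the Table 2-2 range the baseline sits. The high row is too loose in the youngest children and slightly too strict from age 12.

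The consequence is bounded. These are two rows of a descriptive safety display with no decision rule attached, and bradycardia remains visible elsewhere. What is lost is a usable patient count by value for an event of special interest on the 4- and 6-hour post-dose ECGs. How many patients would change category cannot be told from the documents. It should be corrected because the inconsistency is plain and the remedy is cheap.

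**What to change.** In the two heart-rate rows of SAP 2.8.3.1, keep the change of more than 25% from baseline and replace 50 and 100 bpm with the Table 2-2 low and high limits for the patient's age at assessment. If the fixed limits are intended, add a sentence saying why they differ from those for pulse. Showing the counts by age group is optional. This concerns analysis flags only and implies no clinical threshold.

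The cost is a wording change and reuse of the age lookup already needed for pulse rate. Expect more low flags in young children and fewer high flags below age 12.

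### Newly occurring QT/QTc, PR and QRS percentages in SAP 2.8.3.1 keep in the denominator patients who already met the criterion at baseline, contrary to the at-risk rule used for morphology in the same section

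*SAP*

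**What the plan says.** SAP 2.8.3.1 lists notable ECG categories, to be presented by treatment arm. Some are changes from baseline. Others are newly occurring values:

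- "Newly occurring post-baseline QT parameter > 450 ms, > 480 ms, > 500 ms"
- "Newly occurring post-baseline PR > 200 ms and ≤ 220 ms, > 220 ms"
- "Newly occurring post-baseline QRS > 110 ms and ≤ 120 ms, > 120 ms"

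One denominator rule follows for all of them: "The denominator to calculate percentages for each category is the number of patients with both a baseline and a post-baseline evaluation". A newly occurring value is defined as "a post-baseline value that meets the criterion post-baseline but did not meet the criterion at baseline".

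The next item covers newly occurring qualitative (morphology) abnormalities. There the denominator is further limited to patients whose baseline was normal, which the SAP glosses as "i.e. those patients who are at risk of developing this abnormality".

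On the choice of correction, the SAP says: "Data will be summarized using QTcF and QTcB". A regression-based QTcP is added if these remain strongly correlated with heart rate at baseline. Protocol 5.3 (exclusion 2) excludes a QTc above 480 ms by the Fridericia formula. It sets no limit on QTcB.

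**The concern.** For a given threshold, a patient already above it at baseline is ruled out of the numerator by definition but stays in the denominator. The result mixes the incidence among patients who could become new cases with the baseline prevalence of the abnormality. Two adjacent items in one section treat the same idea, a newly occurring abnormality, by different denominator rules, and no reason is given.

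ECG is part of a secondary safety endpoint (SAP Table 1-1) and QT prolongation is an adverse event of special interest (SAP 2.8.1.1). These percentages are likely to be read as incidences. If baseline prevalence differs between treatment groups, for instance because their age mix differs, the percentages are diluted by different amounts and are not directly comparable.

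**Working it through.** The documents state no ECG percentage and no baseline prevalence, so there is no figure of the plan's own to reproduce.

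**1. Dilution for a single threshold.** Let N be the patients with both evaluations, b the share of N already meeting the criterion at baseline, and x the new cases. The plan reports x/N. The at-risk incidence is x/[N(1 − b)]. Hence reported % = at-risk % × (1 − b), and the relative understatement equals b. For an at-risk incidence of 20%:

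| b (assumed) | Reported | At-risk ÷ reported |
|---|---|---|
| 0% | 20% | 1.00 |
| 5% | 19% | 1.05 |
| 10% | 18% | 1.11 |
| 20% | 16% | 1.25 |
| 30% | 14% | 1.43 |
| 40% | 12% | 1.67 |

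In counts, take the 83 treated patients (Amendment 8 rationale), all assumed evaluable, with b = 20%. Then 17 are not at risk and 66 are. With 13 new cases, the plan gives 13/83 = 15.7% and the at-risk figure is 13/66 = 19.7%.

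**2. Where b could be large.** From the SAP formulas, QTcB = QT/RR^(1/2) and QTcF = QT/RR^(1/3), so QTcB/QTcF = RR^(−1/6) with RR = 60/heart rate. At the pulse limits in SAP Table 2-2:

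| Age | Pulse (bpm) | QTcB/QTcF |
|---|---|---|
| 12–18 months | 103–140 | 1.094–1.152 |
| 2–3 years | 92–128 | 1.074–1.135 |
| 15–18 years | 58–92 | 0.994–1.074 |

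At 128 bpm, QTcB passes 450 ms once QTcF exceeds 450/1.135 ≈ 397 ms. At 110 bpm the figure is 450/1.106 ≈ 407 ms. An eligible QTcF of 480 ms corresponds to a QTcB of 480 × 1.135 ≈ 545 ms at 128 bpm. A baseline QTcB above 450, 480 or 500 ms is therefore compatible with eligibility.

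**3. Illustrative sizes of b.** These rest on assumed normal baseline QTcF distributions (mean/SD in ms), which the documents do not supply. QTcB uses the mid-points of the Table 2-2 pulse bands: 121.5 bpm (ratio 1.125) and 75 bpm (ratio 1.038).

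| Assumed QTcF | Share QTcF >450 | Share QTcB >450, 12–18 months | Share QTcB >450, 15–18 years |
|---|---|---|---|
| 395/15 | P(Z > 3.67) ≈ 0.0% | 37% | 0.5% |
| 405/18 | P(Z > 2.50) ≈ 0.6% | 61% | 6% |
| 410/20 | P(Z > 2.00) ≈ 2.3% | 69% | 12% |

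For QTcF >480 and >500 ms the entry exclusion makes b about zero.

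**4. The lower PR and QRS bands.** Here the bias need not be downward. Someone with a PR of 230 ms at baseline and 210 ms later did not meet the >200 to ≤220 ms criterion at baseline and meets it afterwards. The definition counts this improvement as newly occurring. The same holds for QRS moving from above 120 ms into the >110 to ≤120 ms band.

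**The case against.** The strongest reply is that a cumulative proportion of evaluable patients is a clearly defined descriptive summary, and that no test or decision rule rests on it in this phase 1 study. Other planned outputs also fill much of the gap. QT and QTc shift tables at the same 450/480/500 ms cut-points let a reader recover the at-risk counts. The >30 and >60 ms increase rows capture patients already above a limit, and patients with notable values are listed. The SAP itself notes the weakness of Bazett's formula when heart rate fluctuates. All of this stands and limits the importance of the point. It does not remove it, because no shift table is listed for PR, QRS or morphology and the headline percentage stays diluted.

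Three stronger readings are tempting and are not supported:

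- A reader might infer that no patient with an abnormal baseline can be counted. Exclusion is by criterion: a QTc of 460 ms at baseline can still be new at >480 or >500 ms. Nor is the denominator every patient; both evaluations are required.
- A reader might infer that new QTcB prolongation in young children is shown to be understated. The heart-rate arithmetic makes this plausible. But the documents give no baseline QTc distribution, the shares in step 3 swing widely with the assumption, and no ECG percentage by age is planned (SAP 2.1 confines age subgroups to ORR and AEs). A high baseline QTcB share would also largely reflect the Bazett correction itself.
- A reader might infer that the morphology percentage has a numerator that is not contained in its denominator, since a patient with one baseline abnormality may develop another. That follows only if a normal baseline means a wholly normal ECG. The rule is stated to cover each individual finding and is glossed as being at risk of this abnormality. Read per finding, the two match. The wording is ambiguous rather than shown to be wrong.

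**Conclusion.** The inconsistency is real and in the text. For the single-threshold rows (QT/QTc >450, >480, >500 ms; PR >220 ms; QRS >120 ms) the planned percentage can only equal or fall below the at-risk incidence, by the relative amount b. For the lower PR and QRS bands the definition can also count improvement as a new event.

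The size depends on b, which the documents do not give. It is near zero for QTcF >480 and >500 ms. For QTcF >450 ms it is about 0–2% in relative terms under the three assumed distributions. It could be material for QTcB >450 ms, with any effect appearing in the treatment-arm percentages. PR and QRS cannot be sized from the documents. This is a modest reporting defect worth correcting, not evidence that a QT signal has been lost.

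**What to change.** In SAP 2.8.3.1 and the matching table shell:

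1. For each newly occurring category, take as denominator the patients with both a baseline and a post-baseline evaluation who did not meet that criterion at baseline. Show n/m (%), with m the at-risk number.
2. For the PR >200 to ≤220 ms and QRS >110 to ≤120 ms bands, restrict both numerator and denominator to patients at or below the band's lower limit at baseline (200 ms and 110 ms), so that improvement from a higher value is not counted as new.
3. Keep the present denominator for the change-from-baseline rows.
4. For morphology, state that a normal baseline means the specific finding was absent at baseline, and use the same patients in numerator and denominator.

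The cost is a few lines of SAP wording and a denominator change in the table programs. No new data are needed.
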